- d All participants should attend an on-site follow-up visit 90 days (±7 days) after the last IMP administration. SAEs/AESIs (regardless of relationship with study treatment) and IMP-related AEs ongoing at the end of study treatment, and any new IMP-related AEs/SAEs/AESIs will be followed until resolution or stabilization (stabilization is defined as an event ongoing without any change for at least 3 months). If ongoing IMP-related AEs/SAEs/AESIs are resolved or stabilized, no further safety follow-up visit is needed. If IMP related AEs/SAEs/AESIs ongoing, an on-site follow up visit will be performed every 12 weeks (±7 days). Participants who stopped treatment before documented progressive disease should undergo a tumor assessment and an on-site follow-up visit every 12 weeks (±7 days) until radiological disease progression, the start of new anti-cancer therapy, withdrawal of participant's consent, or cut-off date for secondary efficacy endpoints, whichever comes first. After documented progressive disease or the start of a new anti-cancer therapy, participants will be followed until any ongoing IMP related AEs/SAEs/AESIs are resolved or stabilized. Further anticancer treatment will be collected, including date of progression if any.

- e Circulating CEA: As per local laboratory, at pre-screening (no more than 42 days prior to initiation of therapy); at screening (within 7 days prior to initiation of therapy), then during treatment every 8 weeks, at EOT and at the follow-up visit. At screening and first tumor assessment, an additional sample for circulating CEA is requested for central assessment.
- f A fresh tumor biopsy at screening (optional) could be proposed for CEACAM5 expression assessment by IHC (retrospective, results not needed for screening and IMP treatment), WES and RNA sequencing.: Block (preferred option) or 5 slides at 5 µm thickness for IHC and 3 slides at 10 µm thickness (or equivalent quantity) for DNA/RNA evaluation are requested.
- g Plasma for Circulating CEACAM5 (central assessment) at screening within 7 days prior to initiation of therapy (the same day and time as sample for local circulating CEA assessment) and at first tumor assessment (the same day and time as sample for local circulating CEA assessment).
- *h* Includes histologic types, stage at diagnosis, disease extent at study entry.
- *i* Smoking history, tumor mutation status and PD-L1 expression.

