8.2.6.2 Ocular toxicity

• It is recommended that topical artificial tears (and/or hyaluronic ophthalmic gel) are used regularly in all patients treated with tusamitamab ravtansine during the study treatment period.

- The patient should be asked about ocular/visual symptoms at each visit, and ocular evaluation including visual acuity, slit lamp examination under dilatation, and Schirmer's test should be carried out on according to SoA (Section 1.3). Ocular evaluation will be performed at screening, as required during the treatment (ie, on occurrence of ocular symptoms such as blurred vision, photophobia, pain), at the EOT visit, and when relevant at follow-up visit(s). The outcome of the examination should be available before infusion of the next cycle. If ocular symptoms are present, then a formal ocular examination should be performed. In patients with any ocular/visual symptom(s) (eg, blurred vision, photophobia), the ocular evaluation should be repeated once weekly, unless less frequent assessment is recommended by an ophthalmologist, until resolution to Grade 1. Subsequently, the participant should be followed with ocular exam (slit lamp and visual acuity) at each cycle until total resolution of the event.
- Photographs of the cornea are recommended to be taken at the site, if possible, when ocular findings are first documented, and to follow progression when relevant. Tonometry and additional ocular assessment can be performed at the discretion of an ophthalmologist when applicable.

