- Outcome: in case of multiple events with different outcomes, the most severe outcome will be tabulated and selected according to the following order of severity: fatal, not recovered or resolved, recovering or resolving, recovered or resolved with sequelae, recovered or resolved, unknown

In addition, analyses on occurrence and recurrence of corneal events will be provided. An occurrence of corneal event is defined as one or a group of concomitant corneal events. A recurrence is defined as any new occurrence of corneal event starting after a previous resolved occurrence.

- The number of occurrences by participant
- The time to first onset of corneal event will be described using Kaplan-Meier curves. Time to first onset is defined as the time from the date of first IMP administration to the date of the first occurrence of the event. In the absence of an event before the analysis cut-off date, it will be censored at the end date of the treatment-emergent period, analysis cut-off date or date of death, whichever occurs first.

- The time to recovery will be summarized using descriptive statistics in participants who had had at least one recovered or resolved occurrence of corneal event (with or without sequelae), considering the longest duration among all occurrences by participant.
- The time to recurrence will be summarized using descriptive statistics in participants who had had at least one recurrence, considering the shortest time among all recurrences by participant.

Besides the AE categorized as ocular/visual adverse events, all ocular/visual symptoms (coded term) recorded in e-CRF as associated symptom of the reported ocular treatment-emergent adverse events will be reported as descriptive analysis. Same analysis will be done separately for ocular/visual symptoms associated to corneal TEAEs (CMQ)."

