3.6.3.2 Ocular examinations

Schirmer test

Participants reported Schirmer's test will be classified into three classes at baseline: normal ≥ 10 mm, moderate >5 and <10 mm, severe ≤ 5 mm (8). The worst classification between the laterality will be considered. A frequency table of the baseline status with and without anaesthetics will be provided by treatment group for the participants with corneal events (CMQ) during the treatment-emergent period and for the participants without event.

Visual acuity test

Analyses are done on the best corrected visual acuity assessed using Snellen Chart method.

Frequency tables on best corrected visual acuity (BCVA) measured during on-treatment period will be performed separately on all participants and on participants who experienced at least one treatment-emergent corneal event:

- on the worst change from baseline: No worsening versus baseline, Worsening versus baseline (1 to 3 lines decrease versus baseline, or >3 lines decrease versus baseline)
- on the worst absolute value: No change versus baseline, Worsening versus baseline: BCVA equals to 20/40 or better, BCVA worse than 20/40 up to 20/200, BCVA 20/200 or worse.

- on the CTCAE worst vision decrease: No worsening versus baseline, BCVA equals to 20/40 or better or 1 to 3 lines decrease versus baseline, BCVA worse than 20/40 up to 20/200 or >3 lines decrease versus baseline, BCVA 20/200 or worse.
- For participants who had worsening versus baseline on BCVA, the outcome on the last BCVA value will be displayed: Recovered to baseline, Not recovered to baseline, Lost to follow-up or dead with ongoing corneal events

A participant will be considered as lost to follow-up if the participant discontinued the study and did not perform any follow-up visit.

A shift table of the category of the last BCVA value (Normal (20/20 or better), worse than 20/20 up to 20/40, worse than 20/40 up to 20/200 or 20/200 or worse) versus the category of the worst BCVA value (20/40 or better, worse than 20/40 up to 20/200, 20/200 or worse) will be performed for participants who experienced at least one treatment-emergent corneal event.

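### Time to recovery from corneal events is summarised only in participants who recovered, with no censoring, which understates the SAP's own longest-duration measure (minor)

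*SAP*

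**What the plan says.** SAP 3.6.2, in the analyses of occurrence and recurrence of corneal events, gives this rule: "The time to recovery will be summarized using descriptive statistics in participants who had had at least one recovered or resolved occurrence of corneal event". Sequelae are allowed, and the value per participant is chosen by "considering the longest duration among all occurrences by participant".

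Time to first onset, in the same list, is described by Kaplan-Meier with a stated rule: "In the absence of an event before the analysis cut-off date, it will be censored at the end date of the treatment-emergent period". Time to recovery has no such rule.

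The unit is defined as follows: "An occurrence of corneal event is defined as one or a group of concomitant corneal events". The text does not say when a group of concomitant events ends. A recurrence must follow a resolved occurrence.

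Non-recovery is counted in two other places:

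- In the outcome row of SAP 3.6.2, "the most severe outcome will be tabulated and selected according to the following order of severity: fatal, not recovered or resolved".
- In SAP 3.6.3.2, for participants whose best corrected visual acuity (BCVA) worsened, one outcome category is "Lost to follow-up or dead with ongoing corneal events".

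Protocol 8.2.6.2 has participants with ocular symptoms, once resolved to Grade 1, "followed with ocular exam (slit lamp and visual acuity) at each cycle until total resolution of the event". Footnote d of the protocol's study flow chart (1.3.1) lets follow-up of an ongoing event end at stabilisation: "stabilization is defined as an event ongoing without any change for at least 3 months".

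SAP 3.8 carries the SAP's methods to the interim and later analyses where applicable, and updates safety at the end of the study.

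**The concern.** The summary conditions on the outcome that it measures. Because a recurrence needs an earlier resolved occurrence, the participants left out are exactly those with a single, unresolved occurrence. Long events are more likely than short ones to be unresolved at a given date, so the durations that remain are too short as a picture of all participants' longest durations.

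Protocol 2.3.1 names corneal toxicity as the main anticipated risk and describes it as reversible. This is the only estimate of corneal-event duration in SAP 3.6.2. A table limited to those who recovered is a weak test of how fast these events resolve. An event that stabilises without resolving is missing even at the final update if it is the participant's only occurrence.

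**Working it through.** The plan states no recovery time, so there is no figure to reproduce. The check asks what the rule would report under assumed recovery times.

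**Expected numbers.** Protocol Table 1 gives corneal events in 56/186 = 30.1% at this dose and schedule.
- Full study: 0.301 x 38 = 11.4, about 11 participants.
- Interim: 0.301 x 20 = 6.0, about 6 participants.

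**Mechanism, by hand.** Let recovery time T be exponential with median M, and let every participant have follow-up f after onset. With rate r = ln 2 / M:
- share left out = exp(-r f)
- reported median = -ln(1 - (1 - exp(-r f)) / 2) / r

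For M = 6 and f = 12 weeks, exp(-r f) = 0.25, so 25% are left out. The reported median is -ln(1 - 0.375) x 6 / 0.693 = 4.1 weeks instead of 6.

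**Follow-up likely at the interim.** The SAP's version history puts first enrolment on 03-Aug-2022 and SAP approval, before the interim, on 12-Jan-2024: 527 days / 7 = 75 weeks. Two scans at 8-week intervals take 16 weeks. I therefore assumed first doses uniform over 16-75 weeks before the cut, exponential onset with mean 8 weeks, one occurrence each and no deaths. The figures below are the median of T given T no longer than follow-up, by simulation.

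| True median (weeks) | Exponential: reported median (no time contributed) | Gamma, shape 4: reported median (no time contributed) |
|---|---|---|
| 4 | 3.8 (3%) | 4.0 (1.5%) |
| 6 | 5.5 (6%) | 5.9 (3%) |
| 8 | 7.0 (10%) | 7.9 (5%) |

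**Later analyses.** Here follow-up after onset is uniform over 24-48 weeks. Each cell lists the results for true medians of 4/6/8 weeks.

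| Assumption | Exponential | Gamma, shape 4 |
|---|---|---|
| All resolve, no deaths: reported | 4.0/5.8/7.4 | 4.0/6.0/8.0 |
| Median time to death 40 weeks: reported | 3.6/5.1/6.4 | 3.9/5.8/7.7 |
| 10% never resolve, no deaths: reported | 4.0/5.8/7.4 | 4.0/6.0/8.0 |
| 10% never resolve, no deaths: median over all events | 4.7/7.0/9.3 | 4.3/6.4/8.6 |

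The death time and the 10% are assumptions; the documents give neither.

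**Extreme case.** If every participant had only 4-20 weeks of follow-up after onset, the reported medians would be 3.1/3.8/4.3 (exponential) or 3.8/5.4/6.7 (gamma), with 17/29/38% or 6/18/30% contributing no time.

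**Recurrence.** Suppose 40% have a second occurrence, after a mean gap of 6 weeks (assumed), with no deaths. Measured against the first-occurrence median, the SAP's figure is 12-28% longer with 24-48 weeks of follow-up, and between 9% shorter and 17% longer with 12-36 weeks. Against the longest duration per participant it was at or below the truth at every analysis. At the interim it was 4-44% short, over exponential recovery medians of 3-12 weeks, with and without deaths, and an assumed 40-week accrual.

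**The case against.** The SAP states its denominator openly. Duration among those who recovered, with non-recovery counted separately, is a usual descriptive choice in a safety section without testing (SAP 3.6). This stands, and it limits the severity. The outcome rows carry no durations, however, so they do not repair the estimate.

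A reader might infer from the 4-20-week case that this trial will understate recovery time by a third or more. The documents do not support that. The first-step cut-off is timed from the last participant's first dose, so earlier participants have longer follow-up, and the SAP's dates imply follow-up of up to about 75 weeks by the interim.

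A reader might also infer that the table always makes corneal events look too short. That holds only against the longest duration per participant. Taking the longest duration is a worst-case summary, not itself a bias, and with recurrence it can exceed the typical first-occurrence duration.

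Kaplan-Meier also helps least where cut-off truncation is greatest. With about 6 events the upper 95% limit was never estimable in simulation. The SAP does not say that this table will be produced at the interim, which is a futility look at responses.

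Finally, examinations at each cycle stop when cycles stop, so the last ocular assessment alone is a doubtful censoring date, and censoring at death treats death as uninformative. Both points bear on how the change is worded.

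**Conclusion.** The point holds as a minor one. As written, participants whose only corneal occurrence is unresolved contribute no time, and the longest duration per participant is understated. No fixed direction can be claimed relative to the first occurrence.

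For true medians of 4-8 weeks, the shortfall at the interim is about 0.2-1.0 weeks with exponential recovery and at most about 0.1 weeks with gamma recovery. These figures assume the 16-75-week spread of first doses, one occurrence each and no deaths. With 24-48 weeks of follow-up the shortfall is at most 0.6 weeks if all events resolve and nobody dies. With a median time to death of 40 weeks it is 0.1-1.6 weeks, so it need not vanish at the final update. If recovery is quick and few die, it is negligible.

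A reader might infer that the plan hides non-recovery. It does not: the outcome row counts it, and the BCVA table counts it in part. Neither the objective response rate nor the interim rule uses this table.

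**What to change.** Change SAP 3.6.2 as follows.

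1. Define the end of an occurrence as resolution, with or without sequelae, of the last event in its concomitant group.
2. Keep the planned summary, labelled as the longest resolved occurrence per participant. Beside it, show the number of participants with an unresolved occurrence and their time ongoing.
3. At the second-step and end-of-study analyses, and at the first step if enough events have resolved, add a Kaplan-Meier estimate of time from onset to recovery of the first occurrence, in all participants with a treatment-emergent corneal event.
4. Censor unresolved events, including stabilised ones, at the last date on or before the cut-off when the event was known to be ongoing, from an ocular assessment or adverse-event follow-up. Censor deaths with the event ongoing at death, and show their number.
5. Report the median with the log-log 95% CI already planned for time to deterioration (SAP 3.4.1.3). State that it targets the first occurrence, a different quantity from the longest duration.
6. With about 6 events, as at the interim, report only the numbers resolved and unresolved.

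The cost is SAP wording and a few lines of code on dates already collected. The downside is low precision. With 11 events and only 4-20 weeks of follow-up, the upper limit was not estimable in 32/62/80% (exponential) or 6/25/53% (gamma) of simulated trials for true medians of 4/6/8 weeks. With 24-48 weeks it was not estimable in about 3% at most.

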3.6.3 Additional safety assessments

3.6.3.1 Laboratory variables, vital signs and electrocardiograms (ECGs)

The following laboratory variables, vital signs and electrocardiogram (ECG) variables will be analyzed. They will be converted into standard international units.

- Hematology and coagulation:
 - Red blood cells and platelets and coagulation: hemoglobin, hematocrit, red blood cell count, platelet count, prothrombin time (expressed as international normalized ratio)
 - White blood cells: white blood cell count, neutrophils, lymphocytes, monocytes, basophils, eosinophils
- Clinical chemistry:
 - Metabolism: glucose, total protein, albumin
 - Electrolytes: sodium, potassium, chloride, corrected calcium, phosphate
 - Corrected calcium (mmol/L) will be derived using the following formula: measured total calcium (mmol/L) + 0.8 x 0.25 × (4.0 [serum albumin (g/L) × 0.1]), where 4.0 represents the average albumin level.
 - Renal function: creatinine, estimated glomerular filtration rate (eGFR) by the MDRD method, blood urea nitrogen, urea
 - Liver function: alanine aminotransferase, aspartate aminotransferase, alkaline phosphatase, lactate dehydrogenase, total and direct bilirubin
- Vital signs: pulse rate, systolic and diastolic blood pressure, weight, temperature, ECOG Performance status
- ECG variables: heart rate, PR, QRS, QT, and corrected QTc (according to Fredericia)

Data below the lower limit of quantitation/detection limit (LLOQ) will be replaced by half of the LLOQ, data above the upper limit of quantification will be replaced by ULOQ value.

For hematological and coagulation parameters and some selected biochemistry parameters, Sanofi sponsor generic ranges (LLN, ULN) are defined and will be used for grading (see list of parameters in Section 5.5). For other biochemistry parameters, grading will be derived using local laboratory normal ranges.

Quantitative analyses

When relevant, for vital signs and ECG variables, descriptive statistics for results and changes from baseline will be provided for each planned visit and at the worst value (minimum and/or maximum value depending on the parameter) during the on-treatment period. These analyses will be performed using local measurements.

For QRS, QT and QTcF variables, blood pressure and heart rate, mean changes from baseline with the corresponding standard error (SE) will be plotted over time.

Analyses according to Potentially clinically significant abnormality (PCSA) and NCI grading

For laboratory variables, analyses according to NCI grading will be made based on NCI-CTCAE version 5.0. In addition, for laboratory variables for which NCI-CTCAE scale is not applicable, vital signs and ECG variables, PCSA analyses will be performed based on the PCSA list currently in effect at Sanofi at the time of the database lock.

Analyses according to PCSA and NCI grading will be performed based on the worst value during the treatment-emergent period, using all measurements (either local or central, either scheduled, nonscheduled or repeated).

QTcF prolongation will be graded according to NCI-CTCAE version 5.0. The frequency of participants in each grade of QTcF prolongation during the on-treatment period will be summarized. For participants with multiple occurrences of QTcF prolongation during the treatment, the maximum grade by participant will be used.

For laboratory variables, vital signs and ECG variables, the incidence of participants with at least one PCSA during the treatment-emergent period will be summarized regardless of the baseline level and according to the following baseline status categories:

- Normal/missing.
- Abnormal according to PCSA criterion or criteria.

The number (%) of participants with QTcF abnormality worsening during the on-treatment period (worst value per participant) according to baseline value will be displayed.

For laboratory variables graded by NCI-CTCAE version 5.0.

- The number (%) of participants with abnormal laboratory tests at baseline will be presented by grade.
- The number (%) of participants with abnormal laboratory tests during the treatment-emergent period will be summarized by grade. When appropriate, the number (%) of participants with abnormality of any grade and with Grade 3-4 abnormalities will be provided.

For laboratory variables not graded by NCI-CTCAE nor by PCSA, the number (%) of participants with laboratory test outside normal ranges will be provided.

Additional analyses for drug-induced liver injury

The following additional analyses will be performed for drug-induced liver injury:

- For each liver function test (eg, ALT), participants having experienced a PCSA will be summarized considering worst on-treatment value.
- A graph of the distribution of peak values of ALT and AST versus peak values of total bilirubin during the treatment-emergent period will be provided.
- For each liver function test (eg, ALT), participants having experienced a PCSA (eg, ALT >5 ULN) will be summarized using the following categories: Returned to baseline PCSA status (or returned to value ≤ ULN in case of missing baseline) before last IMP dose, Returned to baseline PCSA status after last IMP dose, Never returned to baseline PCSA status, No assessment after elevation. This summary will be performed by categories of elevation (ALT >3, >5, >10, >20 ULN).
- A listing of possible Hy's law cases identified (eg, participants with any elevated AST or ALT of >3 ULN and elevated Total bilirubin >2 ULN, 2 days apart), will be provided, displaying ALT, AST, Total bilirubin and ALP values.

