5.5 GENERIC RANGES FOR HEMATOLOGICAL AND BIOCHEMISTRY PARAMETERS

The current list of generic ranges for hematological parameters (for adults) is provided in the table below:

LBTESTCD	LBTEST	GENDER	LBSTRESU	LBGNNRLO- LBGNNRHI
HGB	Hemoglobin	F	g/L	120-160
HGB	Hemoglobin	Μ	g/L	135-175
LYM	Lymphocytes		10^9/L	1-2
NEUT	Neutrophils		10^9/L	1.8-3.15
PLAT	Platelets		10^9/L	150-350
WBC	Leukocytes		10^9/L	4.5-11
EOS	Eosinophils		10^9/L	0-0.4
BASO	Basophils		10^9/L	0-0.15
MONO	Monocytes		10^9/L	0.18-0.5
HCT	Hematocrit	F	%	0.36-0.46
HCT	Hematocrit	Μ	%	0.41-0.53
RBC	Erythrocytes	F	10^12/L	4-5.2
RBC	Erythrocytes	М	10^12/L	4.5-5.9
INR	INR		Ratio	0.8-1.2

 Table 8 - Generic ranges for hematological parameters

Based on NEJM (N Engl J Med 2004;351:1548-63.): "Laboratory Reference Values". Alexander Kratz. M.D., Ph.D., M.P.H., Maryjane Ferraro. Ph.D., M.P.H., Patrick M. Sluss. Ph.D., and Kent B. Lewandrowski. M.D.

Statistical Analysis Plan12-Jan-2024SAR408701-ACT17241 - tusamitamab ravtansineVersion number: 1

The current list of generic ranges for biochemistry parameters (for adults) is provided in the table below:

LBTEST	LBSTRESU	LBGNNRLO-LBGNNRHI	
Albumin	g/L	35-55	
Blood Urea Nitrogen (BUN)	mmol/L	3.6-7.1	
Corrected Calcium	mmol/L	2.2-2.6	
Chloride	mmol/L	80-115	
Glucose	mmol/L	3.9-7	
Bicarbonate (HCO3)	mmol/L	22-29	
Potassium	mmol/L	3.5-5	
Magnesium	mmol/L	0.8-1.2	
Sodium	mmol/L	136-145	
Phosphate	mmol/L	1-1.4	
Protein	g/L	55-80	
Urea Nitrogen	mmol/L	3.6-7.1	

Table 9 - Generic ranges for biochemistry parameters

6 **REFERENCES**

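### SAP Table 8 is internally inconsistent: the five differential upper limits sum to 6.2 against a white-cell upper limit of 11, and the haematocrit unit does not match its ranges (minor)

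*SAP*

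**What the plan says.** SAP Section 3.6.3.1 states, for haematology, coagulation and some biochemistry parameters, that "Sanofi sponsor generic ranges (LLN, ULN) are defined and will be used for grading (see list of parameters in Section 5.5"). It keeps local laboratory ranges for the remaining biochemistry parameters only, so no local fallback is stated for haematology. It also says that values are converted to standard international units.

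The white-cell rows of Table 8 in SAP Section 5.5 are:

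- "WBC Leukocytes 10^9/L 4.5-11"
- "NEUT Neutrophils 10^9/L 1.8-3.15"
- "LYM Lymphocytes 10^9/L 1-2"
- "MONO Monocytes 10^9/L 0.18-0.5"
- "EOS Eosinophils 10^9/L 0-0.4"
- "BASO Basophils 10^9/L 0-0.15"

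Haematocrit has two rows, both with % as the unit: 0.36-0.46 for women and 0.41-0.53 for men. A note under the table names a published article on laboratory reference values as the source.

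Laboratory variables are graded by NCI-CTCAE version 5.0. Where that scale does not apply, they are assessed against the sponsor's list of potentially clinically significant abnormalities (PCSA), which is not in the documents. For variables covered by neither, "the number (%) of participants with laboratory test outside normal ranges will be provided".

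**The concern.** The total white count and its differential are linked: the parts make up the whole. If the upper limits of the parts add up to much less than the upper limit of the whole, the table calls a total normal while forcing at least one of its parts to be high. Limits of that kind cannot all be right together, and no outside reference is needed to see it.

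The haematocrit rows raise a separate question. A range of 0.36 to 0.46 belongs to a fraction, not to a percentage, so unit and range cannot both be right.

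At stake is the high side of the haematology abnormality tables. In a single-arm study there is no control group in which the same false flags would appear, so an inflated count would be hard to recognise as an artefact.

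**Working it through.** **Inputs.** All limits come from SAP Table 8. That these five cell types make up the white count follows the list in SAP Section 3.6.3.1 and the differential in Protocol Appendix 2 (Table 9). The SAP states no sum of the differential limits; the figure to compare with is its white-cell upper limit of 11.

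| Parameter (10^9/L) | Lower | Upper | Upper / 4.5 |
|---|---|---|---|
| Neutrophils | 1.8 | 3.15 | 0.70 |
| Lymphocytes | 1 | 2 | 0.444 |
| Monocytes | 0.18 | 0.5 | 0.111 |
| Eosinophils | 0 | 0.4 | 0.089 |
| Basophils | 0 | 0.15 | 0.033 |
| Sum | 2.98 | 6.20 | |
| White cells | 4.5 | 11 | |

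**Upper limits.** 3.15 + 2 + 0.5 + 0.4 + 0.15 = 6.20. The gap to the white-cell limit is 11 - 6.20 = 4.80. The white-cell range is 11 - 4.5 = 6.5 wide, and 4.80 / 6.5 = 0.738, or 74%. Only white counts from 4.5 to 6.2 can have all five differentials in range.

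**Example.** Take a white count of 8.0, in range by Table 8. With the other four cell types at their upper limits (2 + 0.5 + 0.4 + 0.15 = 3.05), neutrophils are 8.0 - 3.05 = 4.95, against a limit of 3.15.

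**Lower limits.** 1.8 + 1 + 0.18 + 0 + 0 = 2.98, which is below 4.5. The lower limits show no conflict.

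**A possible cause, by inference only.** Several limits are round percentages of the lower white-cell limit: 1.8 / 4.5 = 40%, 3.15 / 4.5 = 70%, 0.18 / 4.5 = 4%. The upper percentages may have been applied to 4.5 instead of 11. On that assumption the neutrophil upper limit would be 0.70 x 11 = 7.7, and the five upper limits would sum to 6.20 x 11 / 4.5 = 15.2. That exceeds 11, so the conflict would disappear. The SAP does not say how the limits were derived.

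**Haematocrit.** A value stored as 42 (in %) lies above both 0.46 and 0.53, as any normal percentage would. A value stored as 0.42 lies inside both ranges. Written in %, the ranges would be 36-46 and 41-53.

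**Where the upper limits can reach an output.** There are two routes: a grade defined from an upper limit of normal, and the out-of-range counts for variables with neither CTCAE nor PCSA criteria. The second sentence does not itself name Section 5.5, so using Table 8 there is plausible but not stated. Which differentials take either route cannot be settled, because neither the PCSA list nor the CTCAE text is in the documents.

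**The case against.** The strongest reply accepts the addition and contests its reach. Most of it stands.

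- A reader might infer that normal values will be flagged abnormal throughout the haematology tables. The documents do not show this. An output changes only where an affected upper limit is used, and that cannot be fully traced.
- A reader might infer that every participant will have a high haematocrit. That needs values held in %. Section 3.6.3.1 requires conversion to standard international units; if this yields a fraction, nobody is mis-flagged.
- A reader might take 74% as a share of participants. It is a share of interval width; the documents give no distribution of white counts.
- A reader might infer that every table using an upper limit is affected. The SAP's explicit tables of multiples of that limit are the liver analyses. Liver tests appear in neither Table 8 nor Table 9 of the SAP, so they keep local ranges. No error is shown in the other rows.
- A reader might infer that the secondary safety endpoint is distorted. That endpoint counts abnormalities according to CTCAE, whereas the out-of-range counts concern variables that CTCAE does not grade. Only a CTCAE grade built on an affected upper limit could reach it, and the documents show none for a differential.
- The addition proves that the limits are incompatible. It does not prove which of them is wrong.

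The reply does not remove the defect. Table 8 is the operative reference for haematology, and two of its features cannot be right as printed.

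**Conclusion.** The point holds as a minor correction. Table 8's differential upper limits cannot be reconciled with its white-cell upper limit (6.2 against 11), and its haematocrit unit does not fit its ranges. High-side differential flags may be inflated wherever these upper limits are used; by how much cannot be estimated from the documents. The conflict with the white-cell limit assumes that the five listed cell types make up the white count. The effect on haematocrit depends on the unit in which the data are held.

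Decreased-count grading rests on lower limits and is not affected; the neutrophil-decrease entry in Protocol Appendix 6 (Table 10), for instance, starts Grade 1 at the lower limit of normal. The efficacy endpoints and the interim decision, which rests on confirmed responses, do not use Table 8. The safety analyses are descriptive, so no test is affected.

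**What to change.** Before the tables are programmed:

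1. Check the five differential ranges in Table 8 against the source cited beneath it, and correct them so that they are compatible with a white count of 4.5-11. If they cannot be verified, use local-laboratory upper limits for the differential and say so in Section 3.6.3.1.
2. State haematocrit either as a fraction (0.36-0.46 and 0.41-0.53) or in % (36-46 and 41-53).
3. Confirm that the standardised haematocrit unit in the data matches the choice.

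The cost is a documented correction of a few cells in one SAP table and one check of the data unit. No new data are needed.
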